#### 6.5.11 Oxygen Saturation

Oxygen saturation will be measured at screening and when clinically indicated using pulse oximetry.

#### 6.5.12 Imaging for Interstitial Lung Disease (Pneumonitis)

A thorax computed tomography (CT) (or MRI scan) taken at screening as part of the RECIST assessment (see Section 6.2.1) will also be able to document the lung parenchyma status at screening and can be used for comparison with another follow-up scan (with the same methodology as at baseline (CT or MRI), in case clinical symptoms of interstitial lung disease would occur during the trial.

High resolution CT scan/MRI should be performed if clinically indicated by pulmonary symptoms any time during the study.

For any new respiratory symptoms (cough, dyspnea, lower respiratory infection) not clearly explained by other factors (eg, dyspnea associated with substantial drop in hemoglobin), patients should have oxygen saturation measured. If <92%, the high resolution CT /MRI scan of the thorax should be repeated and pulmonary function tests should be performed.

# 6.6 Total Blood Volume

The maximum volume to be drawn in the 3-week periods for Cycles 1 and 2 will not exceed 200 mL. In screening, later cycles and at EOT, volumes drawn will not exceed 100 mL. At the safety follow-up visit, the volumes drawn will not exceed 50 mL.

# 7 SAFETY MONITORING AND REPORTING

# 7.1 Definition of an Adverse Event

The ICH E6(R2) GCP guideline defines an AE as any untoward medical occurrence in a patient or clinical investigation volunteer administered a pharmaceutical product, which does not necessarily have to have a causal relationship with this treatment. An AE can, therefore be any unfavorable and unintended sign (including an abnormal laboratory finding), symptom or disease temporally associated with the use of a medicinal (investigational) product, whether or not considered related to the medicinal (investigational) product.

During the screening period, adverse events include only AEs, which are related to study specific procedures. After enrolment into the study, an AE can include an undesirable medical condition occurring at any time, even if no IMP has been administered. This includes an exacerbation of pre-existing conditions or events, intercurrent illnesses, drug interaction, SARS-CoV-2 vaccines (or any other vaccine) related AEs, or the significant worsening of the indication under investigation that is not recorded elsewhere on the eCRF under specific efficacy assessments. Anticipated fluctuations of pre-existing conditions, including the disease under study, that do not represent a clinically significant exacerbation or worsening will also be considered AEs.

The AE definition includes events occurring from the time of the patient giving informed consent until the safety follow-up 90 days after last study treatment dose.

Any SARSCoV2 vaccine related AEs should be recorded in the Adverse Events eCRF using the following terminology in the verbatim term:

- For general reactions considered to be SARS-CoV-2 vaccine-related, report as "post-SARS-CoV-2 vaccine AEs" (eg, post SARS-CoV-2 vaccine fever).
- For site reactions considered to be SARS-CoV-2 vaccine related, include the words "site" and "post-XX vaccine" (eg, post-SARS-CoV-2 vaccine site pain or post-SARS-CoV-2 vaccine site erythema).

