# 2.2 Endpoints

# 2.2.1 Primary Endpoints

# Phase 1

- Safety: Incidence and severity of AEs and SAEs, including changes in laboratory parameters, vital signs and electrocardiograms (ECGs)
- Tolerability: Dose interruptions, reductions and dose intensity
- The incidence of DLTs with KY1044 as single agent during the first 21 days of treatment
- The incidence of DLTs with KY1044 in combination with atezolizumab during the first 21 days of treatment

# Phase 2

• ORR per Response Evaluation Criteria in Solid Tumors Version 1.1 (RECIST 1.1)

10-Nov-2021 Version number: 1

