#### 6.5.6 Safety Laboratory Tests

All laboratory parameters assessed will be evaluated centrally. However, laboratory tests for safety evaluation, such as hematology, clinical chemistry and coagulation parameters will also be assessed locally at indicated times during each cycle. In exceptional circumstances, the use of local labs may also be considered for assessment of screening laboratory values, after approval by the medical monitor.

Refer to the Schedule of Assessments (Table 6-1, Table 6-2 and Table 6-8) for a summary of the parameters to be evaluated.

More frequent evaluations may be performed at the Investigator's discretion if medically indicated; results should be recorded as unscheduled laboratory assessments.

Laboratory tests will be performed as described below and according to the schedule of assessments.

- All laboratory reports should be reviewed, signed and dated by Investigators. Any clinically significant changes will be recorded as AEs.
- Any single laboratory abnormality without clinical signs or symptoms needs to be repeated before qualifying as an AE.
- All clinically relevant abnormal laboratory tests occurring during the study may be repeated at appropriate intervals until they return to baseline or to a level deemed acceptable by the Investigator or until the abnormality is explained by an appropriate diagnosis.

Full details relating to the methodology of analysis, sample processing, labelling, storage, shipment and destruction procedures will be documented in a laboratory manual.

Test category	Test name	Time of assessment	Approx. mL
			per cycle
			(central assessment
			omy)
Phase 1 and 2 (unl	ess otherwise specified)	I	
Hematology	
 
Hematocrit (HCT), Hemoglobin (Hgb), Reticulocytes, red blood cell count (RBCC), mean cell hemoglobin (MCH), mean hemoglobin concentration (MCHC) and mean cell volume (MCV)
 
Platelets
 
White blood cells with Differential (Basophils, Eosinophils, Lymphocytes, Monocytes, Neutrophils)
 
	
 
Screening a,
 
C 1 b: D1 pre-dose, D2 c, D8, D15
 
C 2 b: D1 pre-dose, D8, D15
 
C 3 b: D1 pre-dose, D8
 
From Cycle 4 b: Day 1 pre-dose (CxD1)
 
EOT
 
	2 mL/sample 2 mL = Screening 8 mL = C1 6 mL = C2 4 mL = C3 2 mL = C4 -EOT
	• HbA1c	
 
Screening a
 
Every 12 weeks: pre-dose (C5D1 etc.).
 
EOT d
 
	

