#### 6.5.7 Vital Signs

Vital signs, including heart rate (HR), blood pressure (BP), respiratory rate, and temperature will be assessed at the screening visit and periodically during the treatment period as described in the Schedule of Assessments.

Heart rate and BP need to be established as a standard assessment (after 5 minutes in the supine position and after 5 minutes standing) during screening only. For all other visits supine position will be used.

During Cycles 1 and 2, BP and HR will be monitored in the clinic every 15 minutes during the infusions of study treatment and every 30 minutes in between the infusions (for combination therapy) and after the last infusion of study treatment for 1 hour and, during Phase 1, before the patients are discharged from the hospital on C1D2. In Phase 1, if the patient does not stay in the clinic for 24 hours on C1D1 (and instead may be released into after hour care per institutional standard), BP and HR need also to be monitored at 6 to 8 hours after the last infusion and/or before the patient is discharged into after hour care. This schedule maybe altered depending on emerging data.

Any changes from baseline in BPs and HR findings judged to be clinically significant by the Investigator will be recorded as AEs. In such cases, vital signs will be repeated at appropriate intervals until they return to baseline or to a level deemed acceptable by the Investigator or until the abnormality can be explained by an appropriate diagnosis.

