#### SAE Reporting Contact Details

The following information is the minimum that must be provided:

- Investigator/reporter's name and contact details;
- Patient identification number;

• Description of the SAE, including criteria for seriousness.

The additional information included in the SAE form must be provided to PRA Drug Safety as soon as it is available. The Investigator must provide an assessment of causality for each event reported. Upon receipt of the initial report, the Investigator's causality assessment will be requested if it was not provided with the initial report.

The Investigator should report a diagnosis or a syndrome rather than individual signs or symptoms. The Investigator must only report AEs that contribute to the seriousness criterion/criteria. Non serious but medically relevant sequelae and the treatments of AEs must be recorded separately, in the narrative section of the SAE report.

A disease progression will not be considered an SAE and will be reported only as a progressive disease in eCRF, and not as an AE/SAE however if there are adverse events related to disease progression, then they along with disease progression should also be reported and recorded as per AE/SAE reporting conventions for this study.

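### Protocol 7.1 counts clinically non-significant fluctuations as AEs, at odds with its neighboring rules, and so lets background variation into the all-causality AE counts

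*Protocol*

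**What the plan says.** Protocol 7.1 opens with the ICH GCP definition of an AE. It then lists what an AE can include after enrolment: among other things, exacerbation of pre-existing conditions and, for the cancer, "the significant worsening of the indication under investigation that is not recorded elsewhere on the eCRF" under the efficacy assessments. The next sentence turns to anticipated fluctuations of such conditions, the cancer included, and says that those "that do not represent a clinically significant exacerbation or worsening will also be considered AEs".

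Other sections set thresholds:

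- Protocol 6.5.6 (laboratory): "Any clinically significant changes will be recorded as AEs". An isolated abnormality without symptoms must also be repeated before it qualifies as an AE.
- Protocol 6.5.7 (vital signs): "Any changes from baseline in BPs and HR findings judged to be clinically significant by the Investigator will be recorded as AEs".
- Protocol 6.5.8 (ECG): the same clinical-significance threshold.
- Protocol 7.1.5: "A disease progression will not be considered an SAE and will be reported only as a progressive disease in eCRF". The sentence goes on to make an exception. Adverse events related to progression are reported, along with the progression, under the usual AE/SAE conventions.

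Incidence and severity of AEs and SAEs is a Phase 1 primary endpoint (Protocol 2.2.1) and a Phase 2 secondary endpoint (2.2.2). SAP 10.7.1 builds the AE tables on TEAEs.

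**The concern.** This sentence helps define the event that the safety endpoint counts. If it is followed, ordinary ups and downs of baseline symptoms, including tumor symptoms, become AEs although the protocol itself calls them anticipated and not clinically significant. If a site takes its cue from the thresholds in 6.5, or reads the sentence as a slip, it will not record them.

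The study is multi-center and non-randomized, and Phase 1 is reported by dose level in cohorts of as few as three patients. SAP 10.5.2.3 plans no sensitivity analysis. A difference in AE counts between dose levels could therefore partly reflect how sites read 7.1, and nothing in the planned output would show it.

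**Working it through.** No arithmetic applies. The check is to compare the passages and then trace a record through to the tables.

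1. **Within 7.1.** For the cancer, the first sentence asks for significant worsening. The second brings in fluctuations of the same disease that are neither a clinically significant exacerbation nor a worsening. The qualifier in the first sentence then has no work to do.

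2. **7.1 against 6.5.6 to 6.5.8.** These sections say that clinically significant laboratory, vital-sign and ECG changes become AEs. If a non-significant fluctuation of a pre-existing condition is an AE anyway, the threshold has no function wherever that fluctuation shows up in one of these measurements. The laboratory repeat rule is the clearest clash, because it is an explicit condition on qualifying as an AE and 7.1 has no counterpart to it.

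3. **7.1 against 7.1.5.** Progression itself goes to the eCRF as progressive disease, with AEs related to it reported separately. Read together, a trivial fluctuation of the cancer is an AE while its progression, taken alone, is not.

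4. **From record to table.** Protocol 9.4.3 and SAP 8.8.2 count an event present before and after first dose as a TEAE only if it worsened in severity. Both gloss this as being reported with a new start date. Baseline signs and symptoms are held as medical history (SAP 8.8.1), and intermittent AEs need an onset for each episode (Protocol 7.1.2). A post-dose swing entered under 7.1 as its own AE therefore carries a new start date and can pass, although a within-grade swing should fail on severity. Once through, it enters the all-causality TEAE tables and the number of events reported (SAP 10.7.1).

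5. **What it does not reach.** A DLT must be clinically relevant, unrelated to disease, and Grade 3 or above apart from the Grade 2 events listed in Table 5-4 (Protocol 5.5). Non-significant fluctuations cannot meet that, so DLT counts and mTPI-2 decisions stand. An event sufficiently explained by an underlying condition is classed as not related (Protocol 7.1.3), so treatment-related summaries are largely protected.

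6. **Size.** Neither document gives a rate for such fluctuations or a background TEAE rate, so there is no figure to reproduce and none to compute.

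**The case against.** The best defense is that broad capture is intended. This is a first-in-human study, the ICH definition at the head of 7.1 has no significance threshold, the list that follows is inclusive rather than exhaustive, and the sentence is worded as an addition. The summary of changes says the AE language in 7.1 was clarified for better data collection. It does not identify this sentence, but intent cannot be excluded. A reader might infer that a negation was certainly lost. That is the likelier explanation, since the qualifiers are shaped like an exclusion, but the documents do not confirm it.

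Nor do 6.5.6 to 6.5.8 say that only clinically significant changes are AEs. They also cover measurements, not symptoms. The conflict is with the purpose of those thresholds and with the repeat rule, not with an express prohibition, and it does not extend to the whole protocol.

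On impact, the defense is partly right. The synopsis describes the Phase 1 primary AE summary in terms of treatment-related events, and there is no formal testing. But Protocol 9.4.3 and SAP 10.7.1 also tabulate all TEAEs, and those tables are exposed. Even if broad capture was meant, the sections would still need aligning.

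**Conclusion.** The sentence is wrong as written, or at the least irreconcilable with its neighbors, and it bears on a primary endpoint definition. The effect is confined to the all-causality AE and TEAE counts and to possible differences in recording between sites. It assumes that some sites follow 7.1 literally, which the documents cannot show.

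Two stronger readings do not hold. One is that the fault contaminates dose escalation or the MTD; the DLT definition rules that out for DLT counts and mTPI-2 decisions. The other is that it adds some stated number of records or pushes TEAE incidence toward every patient; with no fluctuation rate and no background rate in either document, any such figure would be invented.

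**What to change.** Correct the sentence in Protocol 7.1 so that it agrees with the sentence before it, with 6.5.6 to 6.5.8 and with 7.1.5. Most likely this means stating that such fluctuations are not AEs, with the sponsor confirming intent first. Issue a site clarification if sites are still recording. The synopsis puts the end of the clinical phase at Q3 2023 / Q1 2024 and SAP version 3.0 carries a March 2024 date, so that window may have closed.

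Do not delete records already entered. Flag those that rest only on this sentence, and state in the SAP before database lock that the TEAE tables will be shown with and without them. SAP 4.0 already provides for a final version before lock.

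The cost is one protocol sentence, a short SAP addition, some query work to set the flag and a modest amount of extra tabulation. No new data are needed. If the wording changes while recording continues, AE capture will differ before and after the change; the flag and the paired tables make that visible.

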### 7.1.1 Toxicity Management Algorithms (According to SITC)

Management algorithms have been developed to assist Investigators in assessing and managing specific groups of AEs. The Consensus recommendations from the Society for Immunotherapy of Cancer (SITC) Toxicity management working group will be applied, which will include monitoring of organ systems, known to be potentially affected by immune activation. (See Table 5-5).

### 7.1.2 Severity of Adverse Events

Adverse events will be classified for severity by the Investigator according to the Common Terminology Criteria for Adverse Events (CTCAE) v5.0 (Table 7-1).

Grade	Description of severity
0	No change from normal or reference range
1	Mild; asymptomatic or mild symptoms; clinical or diagnostic observations only; intervention not indicated.
2	Moderate; minimal, local or non-invasive intervention indicated; limiting age-appropriate instrumental activities of daily living
3	Severe or medically significant but not immediately life-threatening; hospitalization or prolongation of hospitalization indicated; disabling; limiting self-care activities of daily living
4	Life-threatening consequences; urgent intervention indicated.
5	Death related to AE

### Table 7-1 Common Terminology Criteria for Adverse Events v5.0

AE=adverse event

Changes in the severity of an AE should be documented to allow an assessment of the duration of the event at each level of severity to be performed. Adverse events characterized as intermittent require documentation of onset and duration of each episode and their resolution or outcome.

#### 7.1.3 Causality of Adverse Events

The relationship of an AE to administration of IMPs will be classified by the Investigator (or medically qualified designee) according to the following:

- Related: The temporal relationship of the AE to IMP administration makes a causal relationship possible, and other medications, therapeutic interventions, or underlying conditions do not provide a sufficient explanation for the observed event.
- Not related: The temporal relationship of the AE to IMP administration makes a causal relationship unlikely or remote, and other medications, therapeutic interventions, or underlying conditions provide a sufficient explanation for the observed event.

#### 7.1.4 Follow-up of Adverse Events

During the course of the study all AEs/SAEs will be proactively followed-up for each patient. Every effort should be made to obtain a resolution for all events, even if the events continue after the patient discontinued the study.

Patients will undergo safety assessment at the end of study visit 90 days after the last dose of study treatment.

If any AE remains unresolved after the patient's last visit to the study, detailed evaluation and follow-up should be attempted until the AE has been resolved or a reasonable explanation for its persistence is found.

#### 7.1.5 Serious Adverse Event Assessment and Reporting to the Sponsor

The Investigator (or medically qualified designee) must pursue and obtain information adequate both to determine the outcome of the AE and to assess whether it meets criteria for classification as a serious AE (SAE) requiring immediate notification to PRA Drug Safety.

#### An SAE is any AE that:

- Results in death;
- Is life-threatening (ie, in the opinion of the Investigator, the patient is at immediate risk of death from the AE);
- Results in inpatient hospitalization or prolongation of existing hospitalization (hospitalization is defined as an inpatient admission for 24 hours or longer); hospital admissions for procedures planned before administration of IMP do not need to be reported.

Hospitalization or prolongation of hospitalization in the absence of a precipitating AE is not in itself an SAE. Examples include:

- Social admission (eg, patient has no place to sleep)
- Protocol-specified admission during a clinical study (eg, for a procedure required by the study protocol)
- Optional admission not associated with a precipitating AE (eg, for elective cosmetic surgery)
- Surgery that was planned prior to study enrollment (appropriate documentation is required for these cases) and was not caused by worsening of pre-existing condition
- Hospitalization or prolongation of hospitalization for scheduled therapy of the target malignancy of the study is not considered an SAE
- Results in a persistent or significant disability/incapacity, where disability is a substantial disruption of a person's ability to conduct normal life functions;
- Results in congenital anomaly/birth defect in the offspring of a patient who received IMPs;
- Constitutes an important medical event that may not result in death, be life-threatening, or require hospitalization when, based upon appropriate medical judgement, may jeopardize the patient and may require medical or surgical intervention to prevent one of the outcomes listed in this definition. Examples of such medical events include allergic bronchospasm requiring intensive treatment in an emergency room or at home, blood dyscrasias or convulsions that do not result in inpatient hospitalization, or the development of drug dependency or drug abuse.

The Investigator must report all SAEs, regardless of treatment group or suspected relationship to IMPs, in the eCRF within 24 hours of knowledge of the event being serious.

In case the eCRF is not accessible for any reason at the required reporting time, the Investigator must report the SAE within 24 hours of knowledge of the event being serious using paper form (fax) or by email.

The contact details for alternative reporting are as follows:

#### SAE Reporting Contact Details

The following information is the minimum that must be provided:

- Investigator/reporter's name and contact details;
- Patient identification number;

• Description of the SAE, including criteria for seriousness.

The additional information included in the SAE form must be provided to PRA Drug Safety as soon as it is available. The Investigator must provide an assessment of causality for each event reported. Upon receipt of the initial report, the Investigator's causality assessment will be requested if it was not provided with the initial report.

The Investigator should report a diagnosis or a syndrome rather than individual signs or symptoms. The Investigator must only report AEs that contribute to the seriousness criterion/criteria. Non serious but medically relevant sequelae and the treatments of AEs must be recorded separately, in the narrative section of the SAE report.

A disease progression will not be considered an SAE and will be reported only as a progressive disease in eCRF, and not as an AE/SAE however if there are adverse events related to disease progression, then they along with disease progression should also be reported and recorded as per AE/SAE reporting conventions for this study.

#### 7.1.6 Adverse Events of Special Interest

Adverse events of special interest (AESIs) for atezolizumab are outlined in Appendix 3.

The Investigator must report AESIs in -atezolizumab treated patients, regardless of suspected relationship to IMPs, to PRA Drug Safety **within 24 hours** of knowledge of the event.

Adverse events of special interest for KY1044: Infusion related reactions (IRRs) of Grade 3 severity or above are deemed as Adverse events of special interest (AESIs) with KY1044 and they must also be reported, regardless of suspected relationship to IMPs, to the PRA Drug Safety within 24 hours of knowledge of the event. All other IRRs (Grade 1 and Grade 2) must also be captured in the eCRF as any other AEs recording and reporting conventions. A periodic reassessment of AEs will be conducted as much as possible.

Overdose (please refer to Section 7.2.2 Guidance for Overdose) and pregnancy are considered AESIs with both IMPs.

